1. BACKGROUND / RATIONALE

Each year, 120,000 people sustain a traumatic brain injury (TBI) in Canada¹, with an estimate of 80-90% of TBIs being categorized as mild^{2,3}. Mild TBIs, also known as concussions, have been referred to as the silent epidemic in North America, as the incidence is much higher and effects more persistent than once thought. Concussions can result in a variety of long-term cognitive, psychological, and physical symptoms. Self-reported memory and attention complaints are the most common cognitive effects and may persist for several years post-injury⁴⁻⁶. It has also been reported that in 75% of all sports-related concussions, athletes experience reduced balance and symptoms of dizziness⁷. These residual symptoms may also negatively impact the ability to engage in regular activities of daily living such as work, sports, and driving. Driving safe is a complex task and requires perception of speed and distance, along with good coordination for steering and braking⁸.

After concussion, participants are slower to respond to traffic hazards⁸ and this has been related to increased crash frequency⁹. The goal of the proposed study is to examine the effect of an aerobic and balance retraining program (AET) on common persistent symptoms of concussion using measures of cognition and brain function, mental and physical health, and driving performance.

To date, the majority of randomized controlled trials (RCTs) have used rest and psychological approaches to alleviate persistent concussion symptoms and have focused on providing individuals with recovery-related information, reassurance, or education. Most of these studies have found no benefit or reported inconclusive findings¹⁰. Of the research that has focused on treatment, AET¹¹ has shown to be promising for overall symptom reduction. The conclusions of these studies, however, are limited by the lack of control groups, biased samples, and the inclusion of TBIs of all severities. In addition, many of the interventions were delivered prior to the period when symptoms are typically considered persistent. Controlled studies are needed to test the specific effects of treatment on the persistent symptoms in a post-concussion syndrome sample lasting greater than one month post-concussion. The intervention we plan to test is AET in a controlled/stepwise exercise training program using RCT methodology. Recent evidence indicates that an active rehabilitation program may be useful for individuals with persistent concussion symptoms¹² and that exercise can also be effective at improving mood¹³.

Studies have also shown that levels of brain-derived neurotrophic factor (BDNF) are significantly increased as a result of aerobic exercise in healthy individuals. In particular, preliminary data from our group¹⁴ demonstrated an increase in salivary BDNF levels in a healthy control group following 4 weeks of AET (the same protocol we are proposing). BDNF is a secreted protein that has been shown to play a central role for neural health and brain plasticity^{15,16}. BDNF has been demonstrated to be a useful biomarker of brain injury post-concussion¹⁷ with animal research showing significantly reduced levels of BDNF several hours or days after a concussion¹⁸. Notably, aerobic fitness and BDNF share a relationship that is predictive of memory performance in healthy individuals¹⁹⁻²¹. Also, it is known that executive function and circulating BDNF both decline with age, however, changes in serum BDNF

predicts improvements in cognitive outcomes in response to aerobic exercise in older individuals²².

This provides strong evidence to further examine this intervention in people who are experiencing residual cognitive and/or physical complaints after concussion, but are otherwise healthy. One of the reasons for the lack of response to treatment in previous studies may be, in part, due to the heavy reliance on subjective self-report measures. Therefore, in addition to obtaining self-report measures of persistent complaints, we plan to obtain objective measures of functioning using sophisticated technology, including event-related potentials (ERP) during computerized cognitive tasks, biomarkers (BDNF), force plate measures of balance, and driving simulation measures of participant reaction times under dual tasking situations.

While self-reported cognitive complaints can persist after concussion, they are rarely detected using traditional neuropsychological tests^{23,24}. Using more complex attention and memory tasks, however, slower and less accurate performance can be detected up to several years' post-injury²⁵⁻²⁷. Non-invasive imaging techniques, such as event-related potentials (ERP) can also provide further insight into inefficient neural processing after concussion. ERP is a method of surface electroencephalography (EEG) that non-invasively detects the neural signaling in relation to an event (stimulus or task). In individuals with concussion, ERP studies have previously found deficits in stimulus discrimination²⁸, and inhibitory control²⁹ reflected by increased errors and variable response times in behavior as well as reductions in electrical potentials. Previous studies have found decreased amplitude and increased latency following concussion suggesting a decrease in speed and cognitive resources available for attentional processing²⁹⁻³³.

One of the main goals of recovery from persistent concussive symptoms is the ability to return to daily living. While evaluating performance in daily living activities can be difficult (e.g., driving), we are able to evaluate performance using devices such as driving simulators. Measurements of performance in a simulator (e.g., response time) may become a useful tool as part of a comprehensive assessment for physicians as they recommend return to daily activities.

2. OBJECTIVES / STUDY AIMS

The primary objective of our proposed study is to implement AET to reduce persistent symptoms after concussion. Our secondary objective is to investigate the usefulness of BDNF as a biomarker of persistent concussive symptoms responsiveness to AET.

Our 4 specific goals are to help people with persistent concussive symptoms by:

1. Minimizing the occurrence of persistent cognitive and physical symptoms following concussion.
2. Improving performance and efficiency of neural processing during cognitive tasks.
3. Correlating BDNF levels with severity of symptoms and correlating change in BDNF levels to improvements in physical symptoms and balance.

4. Improving functioning in activities of daily living, such as driving

RATIONALE, SIGNIFICANCE, AND JUSTIFICATION

The clinical significance, rationale, and justification of this collaborative effort is demonstrated by both clinical and research initiatives at treating people with concussion directly in our community. With the recruitment assistance by medical professionals, this project has a strong foundation and the potential to make a direct impact here in Thunder Bay. The group format of the AET is a cost- and time-effective method by which to treat a subgroup of the concussion population who experience long-lasting symptoms. This subgroup is growing as diagnostic protocols are becoming more standardized and the potential persistent effects are becoming general knowledge, especially due to increased media coverage around sport or military related injuries related to concussion. If successful, the AET protocol and salivary BDNF biomarker test may help in the assessment and treatment of persistent concussion symptoms that currently are often treated with rest and education. The findings from the proposed study will help clinicians to also monitor progress to aid in return to play, school, or work decisions, resulting in significant savings to the healthcare system and employer as a result of lost work time. Also, by improving physical health, AET may improve the quality of life.

ASSESSMENT OF OUTCOME/HYPOTHESIS

1. It is anticipated that the concussed participants receiving the AET will exhibit less mental, cognitive, and physical symptoms related to post-concussion syndrome. These signs and symptoms will be measured via the SCAT-3 and the RPSQ scores.
2. It is anticipated that AET will result in increased efficiency of neural processing during cognitive tasks in post measures compared to SC and with less difference than compared to HC compared to pre- intervention comparisons. Cognitive efficiency will be measured by the amplitude and latency of two event related electrical potentials associated with attention and conflict monitoring processing.
3. It is anticipated that concussed participants receiving the AET will exhibit improved balance. This will be measured using the force platform centre of pressure area, displacement, and velocity measures while completing the various static stance positions using the BESS protocol.
4. It is anticipated that concussed participants receiving the AET will exhibit increased improvements in salivary BDNF levels, indicative of an improvement in concussion symptoms. Salivary BDNF will be quantified using the BDNF ELISA assay and changes in pre- vs. post-intervention concentrations will be assessed. Additionally, we hypothesize that lower levels of BDNF upon entry to the study will indicate more pronounced concussive symptoms. This relationship will be determined by correlating the pre-intervention BDNF concentration to measures of the post intervention assessments.

5. It is anticipated that concussed participants receiving the AET will exhibit improved reaction times compared to the SC group during dual tasking scenarios to avoid crashing in dangerous traffic situations.

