4. ELIGIBILITY

4.1 Study Setting Description

This study will be taking place at multiple sites at Lakehead University and around Thunder Bay. Participants will be recruited through the use of recruitment flyers (attached, Section 16.1) posted at various locations as well as on social media (Lakehead University School of Kinesiology Twitter and Facebook). Recruitment flyers will also be posted at Fairway Physiotherapy, as well as other local doctor's offices.

Participants will complete informed consent, screening checklist, questionnaires, ImPACT, and physical measures at the School of Kinesiology, Lakehead University.

Saliva will be collected at the School of Kinesiology, Lakehead University

Oddball and Flaker tasks will be completed at [name] Vision Laboratory, Lakehead University

The driving simulation will be completed at the Centre for Research on Safe Driving, Lakehead University

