4.4 Participant Inclusion Criteria

A participant is eligible for inclusion in the study if the individual meets all of the following criteria:

1. Man or woman aged 18-50 years.

2. Reports at least one PCS symptom that is mild in severity.
3. It has been between two weeks and six months since date of injury.
4. Is able to provide consent in English

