7.2 Description of Study Procedures, Assessments and Participant Activities

Once participants have been randomized into groups, participants will be scheduled to complete the pre intervention assessments at Lakehead University over a period of one week. These assessments will include a physical, cognitive, neuroimaging, biomarker, and driving behaviour assessment. These assessments will also be completed after the intervention in PCS participants, and after eight weeks in HC.

Physical and Cognitive Assessment:

Participants will complete the Immediate Post-Concussion Assessment and Cognitive Testing (ImPACT) at the School of Kinesiology, Sanders building, Lakehead University. The ImPACT will be used as a standard measure of cognitive abilities including: attention, working memory, processing speed, and reaction time. At a mutually agreed upon date and time, participants will meet a member of the research team at the Lakehead University Sanders Fieldhouse. Before beginning the assessments, a member of the research team will verbally restate the participant's rights and confirm that he/she is still willing to participate in the study.

Participants will then be set up at a computer station, where they will follow the on screen instructions for completing the ImPACT battery. Following completion of the ImPACT battery, participants will be asked to stand in a variety of static positions including: narrow based double leg stance, single leg stance, and tandem stance with one foot behind the other. Participants will perform each stance position with his/her eyes open and closed and on a firm and soft surface using the Balance Error Scoring System (BESS) protocol. Each stance will be performed over an AMTI force platform. This approach will be used to measure participant sway, centre of pressure displacement, and to count for the number of perturbation errors induced during the balance test³⁴. The session should last approximately one hour.

Biomarker Assessment:

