11. STATISTICAL CONSIDERATIONS

11.1 Sample Size Calculation

A priori power analysis was conducted to determine that we would have 80% power at alpha = .05 (two tailed) to detect a medium to large effect size with 12 participants in each group, leaving room for a 13% dropout rate. We therefore propose 20 participants per group.

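### Symptom reduction is the primary objective, but its two named scales (SCAT-3, RPSQ) are never scheduled, described or analysed, and no outcome is designated primary

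*Combined protocol and SAP*

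**What the plan says.** Section 2 states: "The primary objective of our proposed study is to implement AET to reduce persistent symptoms after concussion". Hypothesis 1 in the same section expects fewer mental, cognitive and physical symptoms with AET and gives the measure: "These signs and symptoms will be measured via the SCAT-3 and the RPSQ scores". Goal 3 also needs a symptom score: "Correlating BDNF levels with severity of symptoms and correlating change in BDNF levels to improvements in physical symptoms and balance".

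The later sections do not carry the scales forward:

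- 7.1 has measurement rows for ImPACT, BESS, saliva, the oddball and flanker tasks, and the driving simulation.
- 7.2 summarises the visits: "These assessments will include a physical, cognitive, neuroimaging, biomarker, and driving behaviour assessment". Each of these is then described; no symptom questionnaire is.
- 8.1 and 8.2 give a handling route for each scheduled measurement and none for a symptom scale.
- 10 covers saliva, balance, ImPACT, driving and EEG.
- 11.2 applies a group-by-time mixed ANOVA to ERP, balance, BDNF and reaction time.
- 11.1 claims "80% power at alpha = .05 (two tailed) to detect a medium to large effect size with 12 participants in each group", without saying for which outcome.

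Some general text points towards self-report. Section 1 says: "in addition to obtaining self-report measures of persistent complaints, we plan to obtain objective measures of functioning". Section 4.1 says: "Participants will complete informed consent, screening checklist, questionnaires, ImPACT, and physical measures at the School of Kinesiology, Lakehead University". Section 13 calls the questionnaires valid and refers the reader to 7.2.

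**The concern.** The outcome that carries the primary objective is named once and then dropped. The outcomes in hypotheses 2 to 5 (neural processing, balance, BDNF, reaction time) each have a procedure in 7.2 and a place in 11.2. Hypothesis 1 has neither.

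Three things are at stake. First, the trial could finish without a test of its main question, and a baseline symptom score that was not taken cannot be recovered. Second, the symptom-severity part of the BDNF objective has no scheduled score to correlate with. Third, with no primary outcome, nothing in the protocol's analysis text stops a nominal p<0.05 on ERP, sway, BDNF or reaction time from being presented as the main result.

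**Working it through.** **1. Tracing the scales.** In the documents available, SCAT-3 and RPSQ occur only in hypothesis 1 of Section 2. The consent materials were not available and are not relied on. 7.1 alone would be weak evidence, because it also omits the IPAQ, which the plan does use for healthy controls. The weight therefore rests on 7.2 and 11.2.

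**2. Could something else supply the score?**

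- Screening: inclusion criterion 2 reads "Reports at least one PCS symptom that is mild in severity" and names no scale. The PCS checklist in 16.3 has no symptom item, so there is no baseline score from this source.
- ImPACT: 7.2 and 10 describe it as a measure of cognitive functioning, and it is not in the 11.2 list.
- Balance: it bears on physical symptoms but has its own hypothesis (item 3).
- Questionnaires: Section 13 points to 7.2, which describes none. The only questionnaire reproduced is the IPAQ, which measures physical activity.

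None of the 4 outcome groups in 11.2 is a SCAT-3 or RPSQ score.

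**3. The plan's own figure.** The 12 per group in 11.1 cannot be uniquely reproduced: no outcome, test, numerical effect, SD or pre-post correlation is given. For a three-group, two-time interaction, 12 per group gives 80% power at f = 0.32, 0.27 or 0.21 for assumed correlations of 0.3, 0.5 or 0.7. The figure is thus compatible with some analysis, but is not tied to symptoms.

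**4. What the trial could detect on a symptom score, AET vs SC.** From the documents: 20 per group (5.2, 11.1), 13% dropout, two-sided alpha 0.05, 80% power. Completers: 20 × 0.87 = 17.4, taken as 17. Effect sizes and correlations r are assumptions, since the documents give none.

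Unadjusted two-sample t-test: noncentrality d√(n/2), df = 2n − 2.

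| n per group | Detectable d |
|---|---|
| 12 | 1.20 |
| 17 | 0.99 |
| 20 | 0.91 |

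With n = 17, power is 29%, 45% and 62% for true d of 0.5, 0.65 and 0.8.

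Baseline-adjusted: d is replaced by d/√(1 − r²), df = 2n − 3. Change score (the two-group form of the group-by-time interaction in 11.2): d is replaced by d/√(2(1 − r)), df = 2n − 2. With n = 17:

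| r | Adjusted: detectable d | Adjusted: power at 0.8 | Change: detectable d | Change: power at 0.8 |
|---|---|---|---|---|
| 0.5 | 0.86 | 74% | 0.99 | 62% |
| 0.7 | 0.71 | 89% | 0.77 | 83% |

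Completers per group for 80% power:

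| True d | Unadjusted | Adjusted, r = 0.5 | Adjusted, r = 0.7 |
|---|---|---|---|
| 0.8 | 26 | 20 | 14 |
| 0.5 | 64 | 49 | 34 |

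**The case against.** The strongest reply is that this is an execution gap and not a missing outcome. The scales are named, Section 1 states an intention to collect self-report, 4.1 gives questionnaires a location, and Section 10 calls the main analysis a comparison of pre- and post-outcomes, which could include a symptom score. This shows that some symptom collection was probably intended. It does not repair the plan, because none of these sentences gives a scale, a time point or an analysis.

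A second objection is that unadjusted power figures do not describe the planned test. That is fair, so the change-score figures are shown above; they leave the conclusion unchanged. The power figures describe what a symptom comparison could detect. They are not evidence for the omission, which rests on the text.

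Third, hypothesis 4 would correlate baseline BDNF with post-intervention assessments, several of which are scheduled, so that aim is not empty. Its symptom part still lacks a score. 11.2 contains no correlation analysis at all, which also affects the balance part of goal 3, although the balance data themselves are scheduled.

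Fourth, 14.5 commits to trial registration, and a registry entry may name a primary outcome. Its content is not in the documents, so the point here is limited to the protocol and SAP.

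**Conclusion.** The concern holds and must be fixed. Followed literally, 7.2 and 11.2 neither collect nor analyse the measures assigned to the primary objective, no outcome is primary, and 11.1 is tied to no outcome. This conclusion rests on the text and needs no numerical assumption.

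Once a symptom score is made primary, only a large AET vs SC difference is detectable at the planned size. With 17 completers per group, the detectable difference is about 0.7 to 1.0 SD, depending on the analysis and on an assumed pre-post correlation of 0.5 to 0.7.

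**What to change.** **Required.**

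- Add SCAT-3 and RPSQ to 7.1 (pre and post), 7.2 and 8.1, with matching entries in Section 10 and the data abstraction form (16.4).
- In 11.2, add the symptom score to the analysis and name one score from one of the two scales as the primary outcome. The choice is the team's, fixed before data are seen.
- Label ERP, balance, BDNF, ImPACT and reaction time as secondary or exploratory.
- In 11.1, tie the sample size to this outcome and contrast, stating the assumed difference and pre-post correlation.

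**Recommended primary analysis.** Compare AET with SC, the two randomised groups, at the post-intervention assessment, adjusted for the baseline score. At the same n and these correlations, this detects a smaller difference than the change comparison. If the number stays at 20 per group, say that only a large difference is detectable and report the estimate with its confidence interval.

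**Cost.** Wording changes, plus questionnaire time at visits already planned (assumed short; the documents give no duration). There are two downsides. If the chosen score is self-reported, as Section 1 suggests, it comes from participants who know their group (12.3), and Section 1 itself warns against heavy reliance on self-report. The objective measures should therefore stay as supportive evidence. Power is also limited, so more participants may be needed unless the effect or the correlation is large.

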7. STUDY PROCEDURES

7.1 Time and Events Schedule

| Event/Activity/Procedure | Medical appointment | Informed Consent Visit | Pre-intervention assessment A (LU) | Pre-intervention assessment B (LU) | Pre-intervention assessment C (LU) | Pre-intervention assessment D (LU) | AET (3x week)/SC/HC | Post-intervention assessment (A, B, C, D) |
|--------------------------|---------------------|------------------------|------------------------------------|------------------------------------|------------------------------------|------------------------------------|---------------------|---|
| Referral | X | | | | | | | |
| Informed Consent | | X | | | | | | |
| Screening | | X | | | | | | |
| ImPACT | | | X | | | | | X |
| BESS | | | X | | | | | X |
| Saliva | | | | X | | | | X |
| Oddball and Flanker task | | | | | X | | | X |
| Driving Simulation | | | | | | X | | X |
| Intervention | | | | | | | X | |

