13. QUALITY CONTROL AND QUALITY ASSURANCE

We are able to track adherence to the protocol because the intervention requires a visit which is documented in the data abstraction form. All data will be translated into the data abstraction forms. To promote data quality, all team members will be trained in their duties. All questionnaires to be used are valid (see Section 7.2).

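### The hypothesis about BDNF at entry is tested only against post-intervention measures, so no dated analysis tests the association at entry

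*Combined protocol and SAP*

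**What the plan says.** In Section 2, under the outcome hypotheses, item 4 states: "we hypothesize that lower levels of BDNF upon entry to the study will indicate more pronounced concussive symptoms". The next sentence gives the test: "This relationship will be determined by correlating the pre-intervention BDNF concentration to measures of the post intervention assessments". It singles out no measure and states no coefficient, covariates or participant set.

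Specific goal 3 in the same section also plans correlations: "Correlating BDNF levels with severity of symptoms and correlating change in BDNF levels to improvements in physical symptoms and balance". It gives no time point for the level-severity pair and no instrument. The secondary objective concerns BDNF as a marker of how symptoms respond to AET.

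Section 10 describes pre-post comparisons, ANOVAs and a missing-data rule. Section 11.2 describes a group-by-time ANOVA on ERP, balance, BDNF and reaction time. Neither contains a correlation or a covariate.

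On symptom scores, hypothesis 1 says: "These signs and symptoms will be measured via the SCAT-3 and the RPSQ scores". The Background plans self-report ("in addition to obtaining self-report measures of persistent complaints, we plan to obtain objective measures of functioning"), and Section 4.1 mentions questionnaires ("Participants will complete informed consent, screening checklist, questionnaires, ImPACT, and physical measures at the School of Kinesiology, Lakehead University"). The Section 7.1 schedule has saliva before and after the intervention but no row for RPSQ or SCAT-3, and Section 7.2 describes neither.

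**The concern.** The hypothesis is about what BDNF at entry indicates. Its most natural sense is concurrent: participants who arrive with low BDNF arrive with worse symptoms. The stated test replaces the entry symptom status with a status measured after eight weeks of recovery, with AET in one arm. A null result would not refute the entry association, and a positive one would not establish it.

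If the sentence is meant as prognosis, the timing fits but the question changes. The protocol itself expects BDNF to track entry severity, and entry severity may well carry forward to later severity. A raw pre-to-post correlation can therefore appear although BDNF says nothing that the entry symptom score does not already say. It also says nothing about who benefits from AET, because that requires a comparison between the arms.

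At stake is the interpretation of the biomarker results under the secondary objective. With the time point, measure and participant set open, the choice among them could also be made after the data are seen.

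**Working it through.** **1. The plan's own figure.** There is none to reproduce for this analysis. Section 11.1 gives power for an unquantified effect size with group sizes, and no expected correlation. I take from it 20 per group, hence 40 concussed participants, and 13% dropout: 40 × 0.87 = 34.8, so about 35.

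**2. The texts side by side.**

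| Place | BDNF | Symptoms |
|---|---|---|
| Hypothesis 4, claim | entry | concussive symptoms, no time point |
| Hypothesis 4, test | entry | post-intervention measures, none singled out |
| Goal 3 | level, undated | severity, undated |
| Sections 10 and 11.2 | pre and post by group | no BDNF-symptom analysis |

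No dated analysis pairs entry BDNF with entry symptoms. This follows from the text and needs no assumption.

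**3. How far the two pairings can differ (illustration; the documents give no correlations).** Assumed: entry correlation r0 = -0.4; pre-post symptom correlation ρ; direct effect δ of BDNF on later symptoms, in SD; AET effect 0.8 SD; 1:1 arms; two-sided 0.05. Then

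- post = ρ × baseline + δ × BDNF - 0.8 × AET + noise with variance 1 - ρ²
- corr(entry BDNF, post) = (ρ·r0 + δ) / √(1 + δ² + 2ρδ·r0 + 0.8²/4)
- power ≈ Φ(|atanh r|·√(n - 3) - 1.96)

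Entry pairing, n = 40: atanh 0.4 = 0.424; 0.424 × √37 = 2.58; Φ(2.58 - 1.96) = 0.73. Stated pairing with ρ = 0.5, δ = 0: r = -0.20/√1.16 = -0.186, power 0.21. Simulated power agrees with the formula to about 0.01:

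| Entry BDNF paired with | r | Power, n = 40 | Power, n = 35 |
|---|---|---|---|
| entry symptoms | -0.40 | 0.74 | 0.68 |
| post, ρ 0.3, δ 0 | -0.11 | 0.105 | 0.097 |
| post, ρ 0.5, δ 0 | -0.19 | 0.210 | 0.183 |
| post, ρ 0.7, δ 0 | -0.26 | 0.369 | 0.332 |
| post, ρ 0.5, δ -0.1 | -0.27 | 0.40 | 0.36 |
| post, ρ 0.5, δ -0.2 | -0.35 | 0.62 | 0.56 |
| post, ρ 0.5, δ -0.3 | -0.43 | 0.80 | 0.74 |

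The stated test is weaker in most rows and stronger in the last.

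**4. The prognostic reading.** With r0 = -0.4, ρ = 0.5, δ = 0 and n = 35, BDNF adds nothing to entry severity. The raw correlation still rejects in 18% of simulated trials; a regression of the post score on BDNF, baseline score and arm rejects in 4.6%. At n = 40, over r0 -0.4 to -0.5, ρ 0.5 to 0.7 and an arm effect of 0 or 0.8 SD, the figures are 21% to 62% against 4.6% to 5.4%. The raw rejections are not false positives for crude prediction, because the true correlation is not zero (-0.19 in the first case). They mislead only if read as information beyond severity.

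**5. Arm.** Arm is randomised, and entry saliva is taken before the intervention starts, so arm is unrelated to entry BDNF in expectation. It only dilutes the correlation, by 1/√(1 + 0.8²/4) = 0.93.

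**6. Time since injury.** Entry ranges from two weeks to six months after injury (Section 4.4). If time since injury correlated 0.4 with BDNF and -0.4 with symptoms, with no other link, the entry correlation would be 0.4 × (-0.4) = -0.16, and a raw entry test at n = 40 would reject in about 17%. At 0.5 and -0.5 it would be -0.25 and about 35%. A raw entry correlation alone is therefore not enough either.

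**7. Precision.** For an observed r = -0.4 at n = 40: 0.424 ± 1.96/√37 gives 0.101 to 0.746, so the 95% CI is -0.63 to -0.10. The adjusted BDNF coefficient at n = 35 has a simulated 95% half-width of about 0.35 SD in the model of step 4 with δ = -0.3.

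**The case against.** The strongest reply is that the sentence is deliberate. The secondary objective is about responsiveness, so entry BDNF against later status is a plausible prognostic aim. A raw correlation is valid for crude prediction, and nothing in the protocol claims value beyond entry severity. Goal 3 already leaves room for a concurrent correlation, and silence about covariates does not exclude them. All of this stands. It makes the prognostic analysis worth keeping, but it does not supply the missing entry analysis or tie goal 3 to a time point.

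Three stronger readings are tempting and are not supported:

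- A reader might infer that AET confounds the stated correlation. It does not: arm is randomised and adds variance only (step 5).
- A reader might infer that healthy controls enter and create a correlation from the group difference. The documents do not say so, and hypothesis 4 speaks of concussed participants. The participant set is unstated, which is reason to state it, not evidence of pooling.
- A reader might infer that symptom questionnaires will not be collected. The Background, Section 4.1 and Section 13 all refer to self-report or questionnaires. What is missing is their place in the schedule.

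**Conclusion.** The concern holds in a limited form. Followed as written, the plan does not test whether low BDNF at entry goes with worse symptoms at entry. If prognosis is intended, the raw correlation supports crude prediction only: it cannot show information beyond entry severity, and it does not address responsiveness to AET.

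No single figure measures the loss. A reader might set 74% (entry pairing, n = 40) against 18% (stated pairing, n = 35) and conclude that the stated test is simply underpowered. That contrast mixes sample sizes and rests on assumed values; at equal size it is 74% against 21%, or 68% against 18%, and a direct effect of -0.3 SD brings the stated test level or ahead. The mismatch between claim and test depends on none of this.

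The weight is moderate. This is a supporting analysis under the secondary objective, and the randomised AET comparison is untouched.

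**What to change.** In Section 2 (hypothesis 4) and Section 11.2:

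1. Correlate pre-intervention BDNF with the pre-intervention symptom score in concussed participants only, AET and SC combined. Designate either RPSQ or SCAT-3 as the main score. Report the estimate with its 95% CI, and again adjusted for time since injury; the date of injury is already on the data abstraction form (Section 16.4).
2. Keep the pre-to-post analysis as a separate prognostic question: regress the post-intervention score on baseline BDNF, baseline score, arm and time since injury, and report the BDNF coefficient with its CI. This model does not test responsiveness to AET and should not be described as doing so.
3. Add the planned symptom questionnaire to the pre- and post-intervention columns of the Section 7.1 schedule, so that the entry score is assured.

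The cost is a few sentences, schedule rows and short questionnaire time. Saliva is already taken at both time points and no visit is added. Both analyses stay imprecise at 35 to 40 participants, so intervals should carry the interpretation.
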